9. SAFETY

9.1 SPECIFICATION OF SAFETY PARAMETERS

As the sponsor of the Study, INSTITUTION and PRINCIPAL INVESTIGATOR shall be solely responsible for complying, within the required timelines, any safety reporting obligation to competent Health Authorities, IRB/ECs and any participating (co or sub) investigators, as defined in applicable laws and regulations

The Investigator is responsible for monitoring the safety of participants who have enrolled in the study. Safety assessments will be based on medical review of adverse events and the results of safety evaluations at specified time points as described in Section 7.10, Schedule of Events. Any clinically significant adverse events persisting at the end of treatment visit will be followed by the Investigator until resolution/stabilization or death, whichever comes first.

Management of Safety Data

This Study has been designated as an interventional study. As such, all adverse events for Janssen Medicinal Products regardless of causality and special situations excluding those from subjects not exposed to a Janssen Medicinal Product and product quality complaints with or without an adverse event as described in this section will be reported from the time a subject has started study drug until completion of the subject's last study-related procedure (which may include contact for follow-up safety). Serious adverse events will be reported for 30 days after the last dose of study drug.

For the purposes of this study, the Janssen medicinal product is: JNJ-40346527

9.2 DEFINITIONS

9.2.1 ADVERSE EVENT (AE)

An adverse event is defined as any undesirable physical, psychological or behavioral effect experienced by a participant during their participation in an investigational study, in conjunction with the use of the investigational product, whether or not considered intervention-related (21 CFR 312.32 (a)). In general, this includes signs or symptoms experienced by the participant from the time subject has started study drug to completion of the study.

AEs may include, but are not limited to:

- Subjective or objective symptoms spontaneously offered by the participant and/or observed by the Investigator or medical staff.
- Clinically significant laboratory abnormalities.
- A significant worsening of the participant's condition from study entry.
- Disease signs and symptoms and/or laboratory abnormalities existing prior to the use of the study treatment that resolve but then recur after treatment.
- Disease signs and symptoms and/or laboratory abnormalities existing prior to the use of the study treatment which increase in frequency, intensity, or a change in quality after treatment.

9.2.2 SERIOUS ADVERSE EVENT (SAE)

An AE or suspected adverse reaction is considered "serious" if, in the view of either the Investigator, it results in any of the following outcomes:

- Death,
- A life-threatening adverse event,
- In-patient hospitalization or prolongation of existing hospitalization,
- A persistent or significant incapacity or substantial disruption of the ability to conduct normal life functions, or
- A congenital anomaly/birth defect.

Important medical events that may not result in death, be life-threatening, or require hospitalization may be considered serious when, based upon appropriate medical judgment, they may jeopardize the participant and/or participant may require medical or surgical intervention to prevent one of the outcomes listed in this definition. Examples of such medical events include:

- Allergic bronchospasm requiring intensive treatment in an emergency room or at home,
- Blood dyscrasias or convulsions that do not result in in-patient hospitalization, or
- The development of drug dependency or drug abuse.

Hospitalization

For reports of hospitalization, it is the sign, symptom or diagnosis which led to the hospitalization that is the serious event for which details must be provided.

Any event requiring hospitalization or prolongation of hospitalization that occurs during the study must be reported as a serious adverse event, except hospitalizations for the following:

- Hospitalizations not intended to treat an acute illness or adverse event (e.g., social reasons such as pending placement in long-term care facility)
- Surgery or procedure planned before entry into the study. [Note: Hospitalizations that were planned before the start of data collection and where the underlying condition for which the hospitalization was planned has not worsened will not be considered serious adverse events. Any adverse event that results in a prolongation of the originally planned hospitalization is to be reported as a new serious adverse event.]
- For convenience, the investigator may choose to hospitalize the subject for the duration of the treatment period.

Life-Threatening Conditions

Disease progression should not be recorded as an adverse event or serious adverse event term; instead, signs and symptoms of clinical sequelae resulting from disease progression/lack of efficacy will be reported if they fulfill the serious adverse event definition

9.2.3 UNANTICIPATED PROBLEMS (UP)

The Office for Human Research Protections (OHRP) considers UPs involving risks to participants or others to include, in general, any incident, experience, or outcome that meets all of the following criteria:

1. Unexpected in terms of nature, severity, or frequency given (a) the research procedures that are described in the protocol-related documents, such as the IRB-approved research protocol and informed consent document; and (b) the characteristics of the participant population being studied;
2. Related or possibly related to participation in the research (“possibly related” means there is a reasonable possibility that the incident, experience, or outcome may have been caused by the procedures involved in the research); and
3. Suggests that the research places participants or others at a greater risk of harm (including physical, psychological, economic, or social harm) than previously known or recognized.

This study will use the OHRP definition of UP.

9.2.4 SEVERITY OF EVENT

The Investigator will grade the severity of each AE using, when applicable, the current version of the CTCAE v5.0. In the event of an AE for which no grading scale exists, the Investigator will classify the AE as defined below:

- **Mild** (grade 1) – An event that is usually transient in nature and generally not interfering with normal activities
- **Moderate** (grade 2) – An event that is sufficiently discomforting to interfere with normal activities
- **Severe** (grade 3) – An event that is incapacitating with inability to work or do usual activity, or inability to work or perform normal daily activity
- **Life-threatening/debilitating** (grade 4) – An event that puts the participant at immediate or potential risk of death, requires hospitalization, or which drastically impacts a participant’s well-being
- **Fatal** (grade 5)

9.2.5 ASSESSMENT OF CAUSALITY RELATIONSHIP TO STUDY AGENT

For all collected AEs, the clinician who examines and evaluates the participant will determine the AE’s causality based on temporal relationship and his/her clinical judgment. The degree of certainty about causality will be graded using the categories below.

- *Definite* – The AE is clearly related to the study treatment.
- *Probable* – The AE is likely related to the study treatment.
- *Possible* – The AE may be related to the study treatment.
- *Unlikely* – The AE is doubtfully related to the study treatment.
- *Unrelated* – The AE is clearly NOT related to the study treatment.

9.3 EXPECTEDNESS

[name] will be responsible for determining whether an AE is expected or unexpected. An AE will be considered unexpected if the nature, severity, or frequency of the event is not consistent with the risk information previously described for the study agent. The coordinating center will submit reports to Janssen as outlined in the section 9.6.2.

9.4 ADVERSE EVENT LIST(S)

9.4.1 ADVERSE EVENT LIST FOR JNJ-40346527

Detailed information about the risks and expected AEs of JNJ-40346527 may be found in the current edition of the manufacturer's IB. ^a The most frequently reported AEs (occurring in $\geq 20\%$ of participants) by preferred term were pyrexia (11 [52.4%]), nausea (7 [33.3%]), headache (7 [33.3%]), vomiting (6 [28.6%]), and anemia (5 [23.8%]). Severe (CTCAE Grade 3) AEs were reported in 7 (33%) participants and included anemia, lymphopenia, gastric obstruction, peripheral edema, abnormal hepatic function, increased lipase, and hypoalbuminemia. A single subject experienced a CTCAE Grade 4 dyspnea.

9.5 ADVERSE EVENT ASSESSMENT AND FOLLOW-UP

The occurrence of an UP, AE or SAE may come to the attention of study personnel during study visits and interviews of a study participant presenting for medical care, or upon review by a study monitor. All adverse events and special situations, whether serious or non-serious, related or not related, following exposure to a Janssen medicinal product are to be documented by the investigator and recorded in the CRF and in the subject's source records. Investigators must record in the CRF their opinion concerning the relationship of the adverse event to a Janssen medicinal product. Information to be collected includes event description, time of onset, clinician's assessment of severity, seriousness, expectedness, relationship to study product (assessed only by those with the training and authority to make a diagnosis), and date of resolution/stabilization of the event. All AEs occurring while on study must be documented appropriately regardless of relationship. All AEs will be followed to adequate resolution.

Any medical condition that is present at the time that the participant is screened will be considered as baseline and not reported as an AE. However, if the study participant's condition deteriorates at any time during the study, it will be recorded as an AE.

Changes in the severity of an AE will be documented to allow an assessment of the duration of the event at each level of severity to be performed. AEs characterized as intermittent require documentation of onset and duration of each episode.

At each study visit, the Investigator will inquire about the occurrence of AE/SAEs since the last visit. Events will be followed for outcome information until resolution or stabilization.

The Investigator will record all reportable events with start dates occurring any time after the subject has started study drug until completion of the subject's last study-related procedure (which may include contact for follow-up safety). Serious adverse events will be reported for 30 days after the last dose of study drug or until the participant receives alternative therapy for his/her AML, whichever occurs first. Any SAE that occurs after treatment with alternative therapy will be reported only if the Investigator or current treating physician has assessed the SAE as related to the study treatment. Adverse events will be evaluated using the current version of the CTCAE v5.0.

An adverse event as described in this section will be reported from the time a subject has started study drug until completion of the subject's last study-related procedure (which may include contact for follow-up safety). Serious adverse events will be reported for 30 days after the last dose of study drug.

9.6 REPORTING PROCEDURES

9.6.1 OHSU IRB REPORTING OF UNANTICIPATED PROBLEMS AND ADVERSE EVENTS

Unanticipated Problems and AEs will be reported to OHSU IRB according to the policies, procedures and guidelines posted on the [OHSU IRB web site](#).

Events that must be reported by the Investigator to the IRB are detailed in the OHSU IRB **Investigator Guidance: Prompt Reporting Requirements (HRP-801)**. At a minimum, events requiring reporting to the IRB include:

- Any new or increased risk related to the research, including AEs or IND safety reports that require a change to the protocol or consent,
- Publications identifying new risks,
- Data Safety Monitoring Board/Committee letters recommending changes or discussing new risks
- Unanticipated adverse device effect
- Unauthorized disclosure of confidential participant information

9.6.2 CENTRAL REPORTING OF ADVERSE EVENTS FOR MULTICENTER STUDIES

A participating site must report an SAE to the institution's local IRB for action as required, as well as to the OHSU coordinating center study team by phone, fax, or email within 24 hours of learning of the event. The participating center will send the coordinating center materials regarding the SAE, as well as any other study-related documentation requested by the OHSU study team.

The OHSU coordinating center study team will review and submit SAEs to the FDA, OHSU IRB, and any other required contacts as required by the Knight Data Safety Monitoring Plan (DSMP). The PI at the Coordinating Center is responsible for distributing IND and/or IDE Action Letters or Safety Reports, as applicable, to participating institutions for review and submission to their institution's local IRB.

9.6.3 SAE REPORTING

The Sponsor is required to report SAEs with the provided Janssen SAE form. Adverse events to be reported include any UPs (i.e., not listed in the package insert) and any SAEs with a suspected association to the investigational product.

9.6.4 SPONSOR OR ADDITIONAL REPORTING REQUIREMENTS

Unexpected fatal or life-threatening experiences associated with the use of the study treatment will be reported to FDA as soon as possible, but in no event later than 7 calendar days after initial receipt of the information. All other serious unexpected experiences associated with the use of the study treatment will be reported to FDA as soon as possible, but in no event later than 15 calendar days after initial receipt of the information. All events reported to the FDA will also be reported to Janssen Research and Development, LLC as provided in the Research Agreement within 24 hours the investigator becomes aware of the SAE. This information should

be transmitted to Janssen via the Janssen Serious Adverse Event Report Form via secure email to [contact].

Special Reporting Situations

Safety events of interest for a Janssen medicinal product that require expediting reporting and/or safety evaluation include, but are not limited to:

- Drug exposure during pregnancy (maternal and paternal)
- Overdose of a Janssen medicinal product
- Exposure to a Janssen medicinal product from breastfeeding
- Suspected abuse/misuse of a Janssen medicinal product
- Inadvertent or accidental exposure to a Janssen medicinal product
- Medication error involving a Janssen medicinal product (with or without patient exposure to the Janssen medicinal product, e.g., name confusion)
- Suspected transmission of any infectious agent via administration of a medicinal product

These safety events may not meet the definition of an adverse event; however, from a COMPANY perspective, they are treated in the same manner as adverse events. Special situations should be recorded on the Adverse Event page of the CRF.

Any special situation that meets the criteria of a serious adverse event should be recorded on a Serious Adverse Event Report Form and be reported to the COMPANY **within 24 hours of becoming aware of the event.**

Product Quality Complaint (PQC)

A product quality compliant is defined as any suspicion of a product defect related to a potential quality issue during manufacturing, packaging, release testing, stability monitoring, dose preparation, storage or distribution of the product, or delivery system. Not all PQCs involve a subject. Lot and batch numbers are of high significance and need to be collected whenever available.

Examples of PQC include but not limited to:

- Functional Problem: e.g., altered delivery rate in a controlled release product
- Physical Defect: e.g. abnormal odor, broken or crushed tablets/capsules
- Suspected Contamination
- Suspected Counterfeit

PQC Reporting

A PQC may have an impact on the safety and efficacy of the product. Timely, accurate, and complete reporting and analysis of PQC information from studies are crucial for the protection of patients, investigators, and the COMPANY, and are mandated by regulatory agencies worldwide. The COMPANY has established procedures in conformity with regulatory requirements worldwide to ensure appropriate reporting of PQC information. Lot and/or Batch #s shall be collected or any reports failure of expected pharmacological action (i.e., lack of effect). The product should be quarantined immediately and if possible, take a picture.

All initial PQCs involving a Janssen medicinal product under study must be reported to the COMPANY by the PRINCIPAL INVESTIGATOR within 24 hours after being made aware of the event. The Janssen contact will provide additional information/form to be completed.

If the defect for a Janssen medicinal product under study is combined with either a serious adverse event or non-serious adverse event, the PRINCIPAL INVESTIGATOR must report the PQC to the COMPANY according to the serious adverse event reporting timelines. A sample of the suspected product should be maintained for further investigation if requested by the COMPANY.

9.6.5 REPORTING OF PREGNANCY

All initial reports of pregnancy must be reported to the COMPANY by the PRINCIPAL INVESTIGATOR within 24 hours of becoming aware of the event using the Serious Adverse Event Form. Abnormal pregnancy outcomes (e.g. spontaneous abortion, fetal death, stillbirth, congenital anomaly, ectopic pregnancy) are considered serious adverse events and must be reported using the Serious Adverse Event Form.

Any subject who becomes pregnant during the study must be promptly withdrawn from the study and discontinue further study treatment.

No fertility studies have been performed to date. However, JNJ-40346527 may elicit embryofetal toxicity. JNJ-40346527 can only be administered in female and male subjects who practice effective birth control methods. Because the effect of the Janssen medicinal product on sperm is unknown, pregnancies in partners of male subjects exposed to a Janssen medicinal product will be reported by the PRINCIPAL INVESTIGATOR within 24 hours of their knowledge of the event using the Serious Adverse Event Form. Depending on local legislation this may require prior consent of the partner.

Follow-up information regarding the outcome of the pregnancy and any postnatal sequelae in the infant will be required.

9.7 STUDY STOPPING RULES

The overall study will be paused, and appropriate authorities (e.g., IRB, Knight Data and Safety Monitoring Committee) notified if the following events occur:

- Life-threatening grade 4 toxicity attributable to protocol therapy that is unmanageable, or unexpected [detail specific events as appropriate].
- Death suspected to be related to JNJ-40346527.
- As indicated by statistical stopping rules in Section 10.2.4.

10. STATISTICAL CONSIDERATIONS

Refer to Section 3.1, *Description of the Study Design* for a detailed description of the study design and endpoints.

10.1 ANALYSIS POPULATIONS

Most common analysis populations are described below:

Analysis Population	Definition	Endpoint
Intent to Treat (ITT)	Those who consent and are registered for the trial regardless of actual receipt of screening or treatment	Used to report accrual
Evaluable for Safety	Those who received at least one dose of JNJ 40346527	Incidence of DLT and SAE
Evaluable for Response	Those who received at least one cycle of JNJ 40346527 and have response measurements	Best objective response
Evaluable for Overall Survival and Event-Free Survival	Those who received at least one dose of JNJ 40346527 and have survival information	Overall survival

10.2 DESCRIPTION OF STATISTICAL METHODS

10.2.1 ANALYSIS OF PRIMARY ENDPOINT(S)

A Simon 2-stage minimax design will be used to determine best objective response. For each arm, we will enroll 7 patients in the first stage. If there is at least 1 response among the first 7 patients, we will proceed to the second stage and enroll an additional 7 patients. The treatment is considered promising if we have at least 3 responses among 14 patients. We will estimate the best objective response and exact confidence interval using the binomial distribution for each arm separately.

Response assessment will be based on best objective response rates within the first 2 cycles of study drug, including CR, CR with inadequate bone marrow recovery, partial response, stable disease, or progressive disease as defined by Cheson et al.²⁰

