6.3 TREATMENT PERIOD AND MAINTENANCE

Participants will receive JNJ-40346527 at 150 mg PO twice daily in continuous 28-day cycles. Initial response will be assessed by bone marrow biopsy after cycles 1-3 and then every 3 months thereafter. Further study assessments will be performed as outlined in the Section 7.10, Schedule of Events .

Treatment with JNJ-40346527 will continue until disease progression or stopping rules are triggered as a result of either excess toxicity or lack of efficacy (refer to Section 10.2.4).

Disease progression will be defined as any patient with response \geq PR who then loses PR based upon the original pre-treatment marrow sample (PR defined as \geq 50% decrease in marrow blasts to 5-25% of marrow). For example, a patient with 30% blasts on pre-treatment

marrow who achieved CR with 4% blasts and then was found to have 6% blasts with continued hematologic recovery on subsequent marrow (PR) would remain on trial until subsequent marrow blasts were >15%, or with loss of hematologic response. Patients with stable disease who continue to receive clinical benefit per PI review may remain on study drug.

If a participant achieves a complete remission (CR) and is deemed a candidate for allogeneic stem-cell transplant, JNJ-40346527 should be discontinued 7 days before initiation of the conditioning regimen. Treatment with JNJ-40346527 may be resumed 30-100 days after the transplant if patients has a relapse of their disease, no active GVHD, and after review by the PI.

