7.2.5 BONE MARROW EXAM

Bone marrow aspirate must be collected at the visits outlined in the Section 7.10, Schedule of Events (Cycle 1 Day 29, Cycle 2 Day 29, Cycle 3 Day 29, and every 3 months following Cycle 3 Day 29. Additional bone marrow evaluations may occur if clinically indicated at the discretion of

the investigator (e.g., at the time of suspected disease progression or disease remission.)

Bone Marrow Aspirate will be collected to assess:

- Hematopathology review
- myeloid:erythroid ratio per standard of care
- Cellularity (%)
- blast quantification per standard of care.
- Cytogenetics will be performed as standard of care.
- Pharmacokinetic assay described in Section 7.3.1. (5-8ml in sodium heparin)
- Flow cytometry: as standard of care per institutional standards and exploratory analysis described in Section 7.3.2.

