8.2 RESPONSE CRITERIA FOR AML

The objective response rate will be defined as \geq PR, including cytogenetic and molecular responses when applicable, and will be determined at the end of each cycle.

Complete Remission (CR)*:

- Bone marrow blasts < 5%;
- Absence of blasts with Auer rods;
- Absence of extramedullary disease;
- Absolute neutrophil count $>1 \times 10^9/L$ (1000/ μ L);
- Platelet count $> 100 \times 10^9/L$ (100,000/ μ L);
- Independence of red cell transfusions

Morphologic CR:

- Bone marrow blasts <5%;
- Absence of blasts with Auer rods;
- Absence of extramedullary disease;
- No hematologic recovery required

Partial Remission

- Relevant in the setting of phase 1 and 2 clinical trials only;
- All hematologic criteria of CR;
- Decrease of bone marrow blast percentage to 5% to 25%;
- Decrease of pretreatment bone marrow blast percentage by at least 50%

Cytogenetic Complete Remission (CRc):

- Reversion to a normal karyotype at the time of morphologic CR in cases with an abnormal karyotype at the time of diagnosis; based on the evaluation of 20 metaphase cells from bone marrow.

Molecular CR (CRm):

- Molecular studies are negative (i.e., normal molecular markers in persons with previously abnormal molecular studies (e.g. c-KIT, NPM1, FLT3).

CR with incomplete recovery (CRI): • All CR criteria except for residual neutropenia ($< 1 \times 10^9/L$ [$1000/\mu L$]), or thrombocytopenia ($< 100 \times 10^9/L$ [$100,000/\mu L$]).

Stable disease (SD) Not fulfilling either PR or PD criteria and clinical stability

Progressive disease (PD) Increase in blasts by $\geq 50\%$

Definitions of response criteria are amended from Cheson et al.²⁰

*All criteria need to be fulfilled; marrow evaluation should be based on a count of 200 nucleated cells in an aspirate with spicules; if ambiguous, consider repeat exam after 5 to 7 days; flow cytometric evaluation may help to distinguish between persistent leukemia and regenerating normal marrow; a marrow biopsy should be performed in cases of dry tap, or if no spicules are obtained; no minimum duration of response required.

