10.2.4 INTERIM ANALYSIS AND STOPPING RULES

This study will consist of 2 stopping rules: one for futility (lack of efficacy) and another for excess toxicity.

For futility, we will follow the stopping rule based on the Simon's 2-stage design with the minimax criteria. Specifically, if there is no response among the first 7 patients after receiving 2 cycles of study agent, the arm will not proceed to the second stage.

[figure not shown]
For excess toxicity, we will suspend enrollment if the lower 90% confidence interval for Grade 3 or higher treatment-related toxicity exceeds 30% (considered acceptable dose-limiting toxicity (DLT) incidence). We will then conduct a comprehensive toxicity evaluation and consult with the Knight Cancer Institute's Data and Safety Monitoring Committee for guidance on possible modifications of the protocol, including termination of one or more of the arms, dose modification, and/or changes in eligibility criteria.

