10.3 SAMPLE SIZE, POWER, ACCRUAL RATE AND STUDY DURATION

10.3.1 SAMPLE SIZE AND POWER

The sample size for each group was derived according to the 2-stage design with minimax criteria using the following parameter settings: 1) 80% power; 2) 5% significance level; 3) historical response rate of 5% (poor response), and 4) desired response rate of 30% (promising response).²¹ The sample size and power analyses were conducted using PASS 14 software (<http://www.ncss.com/software/pass/>). Based on the expected accrual rate of 14 participants per year, we anticipate this trial to take 36 months (24 months of accrual and 12 month of minimum follow-up).

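### The primary response window is three cycles in Section 3.2.1 and two in Section 10.2.1, so a first response at cycle 3 may or may not count towards 3 of 14

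*Combined protocol and SAP*

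**What the plan says.** The endpoint table in Section 3.2.1 starts the clock for best objective response rate at the first dose and ends it after three cycles.

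Section 10.2.1 gives the decision rules for each arm. For stage 1: "If there is at least 1 response among the first 7 patients, we will proceed to the second stage". For the final count: "The treatment is considered promising if we have at least 3 responses among 14 patients". It then states: "Response assessment will be based on best objective response rates within the first 2 cycles of study drug". That sentence is not limited to the interim look.

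Section 10.2.4 gives the futility look a two-cycle window. An arm does not go on to stage 2 "if there is no response among the first 7 patients after receiving 2 cycles of study agent".

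The assessment schedule runs past cycle 2. Section 7.2.5 lists marrows at "Cycle 1 Day 29, Cycle 2 Day 29, Cycle 3 Day 29", Section 6.3 says "Initial response will be assessed by bone marrow biopsy after cycles 1-3", and under Section 8.2 objective response "will be determined at the end of each cycle", with no last cycle given.

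Section 10.3.1 gives the historical rate (5%) and the desired rate (30%) without saying over how many cycles either is measured.

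**The concern.** The two sections define different primary endpoints. They differ by exactly one scheduled marrow, Cycle 3 Day 29. A participant whose first partial remission or better appears there is a responder under Section 3.2.1 and a non-responder under Section 10.2.1.

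The margin for declaring an arm promising is a single participant, so this difference can decide an arm's conclusion. With both definitions in the approved text, the window could be settled after the responses are known. The documents do not suggest that anyone intends this, but they do not prevent it.

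There is a second consequence. The stage 1 rule has only one stated window, two cycles, and is not contradictory in itself. If Section 3.2.1 governs the final count, however, the two looks use different windows, and the single-rate calculation behind the sample size no longer describes the trial.

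**Working it through.** **Inputs.** Stage 1: 7 participants, stop at 0 responses. Final: 14 participants, promising at 3 or more (Section 10.2.1). Rates 5% and 30%, 80% power, 5% significance level (Section 10.3.1; one-sided per the synopsis). Windows: two cycles (Sections 10.2.1 and 10.2.4) or three (Section 3.2.1).

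**Step 1: reproduce the stated design.** With one response probability p at both looks,

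P(promising) = Σ over x = 1 to 7 of P(X = x) × P(Y ≥ 3 − x), with X and Y independent Binomial(7, p).

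- p = 0.30: 0.2471 × 0.6706 + 0.3177 × 0.9176 + 0.3529 = 0.810. Early stopping: 0.70^7 = 0.082.
- p = 0.05: 0.2573 × 0.0444 + 0.0406 × 0.3017 + 0.0038 = 0.027.

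Power is 81.0%, type I error 2.7%, and an arm with a true 30% rate stops at stage 1 with probability 8.2%. A search over two-stage designs returns 7 + 7 with these cutoffs as the minimax design. The sample size is correct for a single window.

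**Step 2: the one-patient flip.** Two responses by cycle 2 plus one first seen at cycle 3 is 2/14 = 14.3% (not promising) by Section 10.2.1 and 3/14 = 21.4% (promising) by Section 3.2.1. No assumption is needed.

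**Step 3: how often it could matter.** Let f be the share of three-cycle responders who first respond in cycle 3. The documents give no value; 10%, 20% and 30% are assumptions, and at f = 0 nothing changes. Let p2 and p3 be the response probabilities by cycles 2 and 3, so p2 = p3(1 − f). With a two-cycle interim and a three-cycle final count,

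P(promising) = Σ over x = 1 to 7 of P(X = x) × (1 − f^x) × P(Y ≥ 3 − x), with X and Y Binomial(7, p3).

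The factor 1 − f^x is the chance that at least one of the x stage 1 responders responded by cycle 2. If both looks use two cycles, the Step 1 formula applies with p = p2, and early stopping is (1 − p2)^7. The three-cycle count is never below the two-cycle count. So, with the same two-cycle interim, the probability of opposite verdicts is the difference between the two results.

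*If 30% is a three-cycle rate (p3 = 0.30):*

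| | f = 10% | f = 20% | f = 30% |
|---|---|---|---|
| p2 | 0.27 | 0.24 | 0.21 |
| Power, two cycles at both looks | 74.1% | 65.6% | 55.7% |
| Power, two-cycle interim, three-cycle final | 79.0% | 76.3% | 72.7% |
| Opposite verdicts (difference) | 4.9% | 10.7% | 17.0% |
| Early stop on a two-cycle interim | 11.0% | 14.6% | 19.2% |

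Three cycles at both looks keeps power at 81.0%.

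*If 5% and 30% are two-cycle rates (p3 = p2/(1 − f)):*

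| | f = 10% | f = 20% | f = 30% |
|---|---|---|---|
| Power, two-cycle interim, three-cycle final | 85.1% | 88.3% | 90.4% |
| Opposite verdicts (that power minus 81.0%) | 4.1% | 7.3% | 9.4% |
| Type I error, two-cycle interim, three-cycle final | 3.4% | 4.4% | 5.6% |
| Type I error, three cycles at both looks | 3.6% | 4.8% | 6.7% |

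Type I error passes 5% at f of about 26% with mixed windows and about 21% with three cycles at both looks. Two cycles at both looks leaves the design unchanged.

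**The case against.** The best defence is that endpoint definitions belong in Section 3, so three cycles governs, and that Section 10.2.1 simply carries over the two-cycle interim wording of Section 10.2.4. The marrows after each of cycles 1 to 3 fit that reading. Section 10 also opens by sending the reader back to Section 3.1 for design and endpoints. This does not settle the matter. Section 3.1 gives no response window and itself refers to Section 10 for statistical methods. The two-cycle sentence stands in the primary analysis section after the 3-of-14 rule, with no restriction to the interim. A two-cycle interim with a three-cycle final count would be a coherent plan, but the documents do not state it.

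A second objection is that the late-response share is unsupported and could be close to zero, where the mismatch has almost no effect. That stands: the percentages are a sensitivity range, not an estimate. The 2/14 versus 3/14 flip does not depend on them.

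Third, the type I error risk is modest. That also stands. The attained 2.7% leaves slack, and among the shares shown only 30% breaches 5%.

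Finally, this is a small non-randomised trial of preliminary efficacy with a correctly computed design. That limits the consequences, but the conflict still lies in the count that decides each arm.

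**Conclusion.** The concern holds and should be fixed. The primary endpoint has two written windows, and one participant first responding at cycle 3 can reverse an arm's conclusion. This follows from the text and the cutoff alone.

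The effect on operating characteristics depends on two things the documents do not give: the share of responders who first respond in cycle 3, and the window to which the 5% and 30% rates refer. The direction is therefore unknown. Power can fall below the stated 80%, or type I error can rise, in some cases above 5%. If the design rates match one window used at both looks, nothing changes. The sample size calculation itself is not at fault.

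**What to change.** - Put one window for the final 3-of-14 count in both Section 3.2.1 and Section 10.2.1.
- Say in Section 10.2.4 whether the stage 1 look uses that same window.
- Say in Section 10.3.1 which window the 5% and 30% rates refer to. If the interim and final windows differ on purpose, report the resulting power and type I error.
- For clarity, state that a response-evaluable participant (Section 10.1) with no response by the end of the chosen window counts as a non-responder.

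Make the change before response data are reviewed.

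The cost is protocol wording. No visit or procedure is added, because all three marrows are already scheduled. If three cycles is chosen for both looks, the stage 1 decision in an arm with no response by cycle 2 comes about one 28-day cycle later. It could be later still with the treatment delays (up to 28 days, Section 6.2.2) and assessment windows (7 days either way, Section 7.5) already allowed.
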